### 7.4 Study Product Compliance

Compliance with study treatment will be assessed at Visit 2 for monotherapy and Visit 3 and Visit 4 for the combination therapy. The PI must instruct patients to return the medications at each visit. The amount of study medication taken by the patient will be derived by counting the number of tablets in the blister returned and will be recorded in the source document and in the electronic case report form (eCRF).

Adherence to treatment will be measured through treatment compliance which will be calculated by using the below formula:

 $\frac{\textit{number of doses taken during the study}}{\textit{number of doses to be taken during the study}} \times 100$ 

MENARINI	Corporate Medical Department		ent
	]	Protocol Template	
Identification Number	Version Number	State	Effective date
FORM-000050125	2.0, CURRENT	Effective	08 Jan, 2021

Study Code: MEIN/21/AmNe-Hyp/001

A patient who has taken at least 80% and no more than 120% of the required study medication intake since the last visit will be considered as compliant.

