### **10 WITHDRAWAL CRITERIA**

### Withdrawal of monotherapies or the study treatment

Withdrawal from the monotherapies or study treatment refers to any patient who does not receive the complete course, ie. when no further planned dose is administered from the date of withdrawal. A patient withdrawn from the monotherapies or study treatment may continue further study procedures (safety) planned in the Study Protocol, as deemed appropriate by the Investigator once the safety of the patient is recovered/reassured.

A patient's study treatment or monotherapies may be discontinued for any of the reasons below. In addition to the scheduled visits, patient who have been withdrawn from study treatment or monotherapies may also undergo additional medical follow-up at the discretion of the Investigator.

MENARINI	Corporate Medical Department Protocol Template		ent
Identification Number	Version Number	State	Effective date
FORM-000050125	2.0, CURRENT	Effective	08 Jan, 2021

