### Withdrawal of patient from the study

The patient may withdraw from the study at any time without explanation, without losing the right to future medical care. The participation of the patient may, at any moment, be terminated by the Investigator, if considered appropriate.

A patient can be withdrawn during the study for any of the following reasons:

- Any AE, which required treatment and study termination for the patient according to the Investigator's judgment.
- Abnormal renal function or liver enzyme parameters as described in Section 8.2.3.
- Patient becomes pregnant during the study.
- Request of the patient (without giving any reason).
- Investigator deems it to be in the best interest of the patient to discontinue.
- Failure to adequately comply with the dosing, evaluations, or other requirements of the study.
- If the patient meets an exclusion criterion (newly developed or not previously recognized) that precludes further study participation.
- Use of any prohibited medication that in the opinion of the Investigator or Sponsor necessitates the patient being withdrawn.

The reason for the withdrawal of study treatment, or withdrawal from the study must be well documented in the source documents and in the eCRF page and should capture the date and the specific underlying reason for discontinuation of study treatment or patient discontinuation/withdrawal.

MENARINI	Corporate Medical Department		
	Р	Protocol Template	
Identification Number	Version Number	State	Effective date
FORM-000050125	2.0, CURRENT	Effective	08 Jan, 2021

*Study Code:* MEIN/21/AmNe-Hyp/001

Patients who discontinue from the study early will be asked, anyway, to complete all the assessments of Visit 4. Patients may discontinue the study treatment, but remain in the study for follow-up, especially for safety study endpoints (if applicable).

If a patient has been discontinued/withdrawn due to an AE, the Investigator must immediately notify the relevant pharmacovigilance contact (see Section 9.9) and should be followed-up until the AE is resolved or the Investigator deems further observations or examinations as no longer medically indicated.

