15. STUDY MEDICATION COMPLIANCE

Compliance to study medication (i.e., monotherapy and/or combination therapy) will be presented for the mITT and SAF populations.

A table consisting of summary statistics for percent compliance along with the number and percent of patients with compliance in each of the following groups:

- Low: percentage of compliance <80%
- Normal: percentage of compliance =>80% - <=120%
- High: percentage of compliance >120%

on SAF population for Monotherapy, and mITT as well as SAF populations for Combination Therapy. By visit (Visit2 and Visit 3) and overall compliance will be produced for Combination Therapy.

A listing of drug accountability will be presented on mITT and SAF populations by phase to account for all drug distributed to each patient, including the box number, total number tablets dispensed, returned, consumed, lost (if any), percentage compliance and compliant (yes/no).

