15.1. Derivations

Monotherapy and Combination Therapy compliance with study drug based on the drug accountability data will be calculated as the number of tablets taken x 100 / expected number of

Document: \\needc-vnasc01\Biosdata\Menarini\NebAml\ZZA67778\Biostatistics\Documentation\SAP\SAP_Menarini_MEIN21AmNe-Hyp001_Final_V1.0

Author: [name]

Version Number:

Final V1.0

Version Date:

11Nov2022

Template No.: CS_TP_BS016 Revision 7

Reference: CS_WI_BS005

Effective Date: 01Nov2021

tablets which should have been taken expressed as a percentage.

For Monotherapy, the expected number of tablets to be taken = (Treatment End Date – Treatment Start Date) + 1.

For Combination Therapy, the expected number of tablets to be taken = 2 * ((Treatment End Date – Treatment Start Date) + 1).

For patients who permanently stop the study medication (i.e., monotherapy and/or combination therapy), the expected number of tablets will be calculated up-to the date of study withdrawal.

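### SAP 15.1 counts expected tablets to study withdrawal for patients who stop treatment, so adherence is understated for those who leave the study later and undefined for those who complete Visit 4

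*SAP*

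**What the plan says.** SAP 15.1 defines compliance as tablets taken over tablets expected, as a percentage. The monotherapy denominator is given by "For Monotherapy, the expected number of tablets to be taken = (Treatment End Date – Treatment Start Date) + 1", and the combination denominator is twice the same interval because two tablets are taken daily. The last sentence of the section sets a different end point for patients who permanently stop: "the expected number of tablets will be calculated up-to the date of study withdrawal".

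Protocol section 10 has separate headings for withdrawal of treatment and withdrawal from the study. Under the first, a patient taken off treatment "may continue further study procedures (safety) planned in the Study Protocol, as deemed appropriate by the Investigator". Under the second, "Patients may discontinue the study treatment, but remain in the study for follow-up".

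Adherence is a listed secondary endpoint. Protocol 7.4 regards as compliant "A patient who has taken at least 80% and no more than 120% of the required study medication intake since the last visit". SAP 15 reports summary statistics for percent compliance, three classes whose lowest is defined by "Low: percentage of compliance <80" per cent, and a yes/no compliant flag in the accountability listing. For combination therapy the table is produced on the mITT and Safety populations, by visit and overall.

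**The concern.** The two end points agree only when a patient leaves the study on the day treatment stops. When the patient stays on, the last sentence of SAP 15.1 adds expected tablets for days after treatment had ended. If an adverse event led the investigator to end treatment, none were due on those days. Two patients with identical tablet-taking then get different adherence scores because one left the study later than the other. The score mixes how well a patient took the drug while on it with how long the patient was followed afterwards.

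For a patient who stops drug and attends Visit 4 as a completer, the difficulty is different: no date of study withdrawal exists, and the SAP does not say what to use instead. The two adherence tables meet this differently. The mITT population requires Week 8 DBP data, so an early stopper in it will usually be this undefined case. The Safety population can contain both kinds.

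What is at stake is the mean percentage, the Low/Normal/High counts and the compliant flag for a secondary endpoint.

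**Working it through.** The documents give no compliance figure to reproduce, so the check applies the SAP 15.1 rule directly.

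**Inputs.** Two tablets a day in the combination phase and one in the run-in (SAP 15.1). Combination phase of 8 weeks, 56 days, or 60 with the +4-day window at Visit 4 (Protocol 5.1). Run-in of 4 weeks, 28 days. Low class below 80% (SAP 15).

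**Formula.** Let the patient take every tablet to stop day s and withdraw from the study on day T, with T later than s.

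- Rule for permanent stoppers: 100 × 2s / 2T = 100 × s/T. The factor 2 cancels, so the run-in gives the same expression.
- Count to last dose: 100 × 2s / 2s = 100% for every s.
- Low requires s/T < 0.8, that is T > 1.25s, that is (T − s) > 0.25s. Time off drug must exceed 25% of time on drug.

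**Combination phase, T = 56 (112 tablets expected):**

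| Stop day s | Taken | Score to study withdrawal | Class | Score to last dose |
|---|---|---|---|---|
| 14 | 28 | 28/112 = 25.0% | Low | 100% |
| 28 | 56 | 56/112 = 50.0% | Low | 100% |
| 42 | 84 | 84/112 = 75.0% | Low | 100% |
| 44 | 88 | 88/112 = 78.6% | Low | 100% |
| 45 | 90 | 90/112 = 80.4% | Normal | 100% |
| 50 | 100 | 100/112 = 89.3% | Normal | 100% |

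With T = 60 (120 tablets), the first stop day classed Normal is day 48: 96/120 = 80.0%.

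**A 28-day period (the run-in, or one visit interval), T = 28:** s = 14 gives 50.0% (Low), s = 22 gives 78.6% (Low), s = 23 gives 82.1% (Normal).

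**Which patients these rows describe.** They follow from the SAP text for a patient who formally withdraws from the study on day T. For a patient who completes Visit 4 on day 56 they hold only if Visit 4 is treated as the withdrawal date, which the SAP does not say. If the general formula applied to that patient instead, with treatment end taken as the last dose, the score would be 100%.

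**Effect on the mean.** The documents do not say how many patients would stop drug and stay. Suppose a fraction p stops between days 14 and 28 with full intake and is counted to day 56. The mean falls by p × (100 − 50) to p × (100 − 25).

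- p = 5% (assumed): 0.05 × 50 = 2.5 to 0.05 × 75 = 3.75 points, and 5 points more in the Low class.
- p = 10% (assumed): 5 to 7.5 points, and 10 points more in the Low class.
- Per 1% of patients: 0.5 to 0.75 points. With no such patients there is no effect.

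**The case against.** The strongest reply is that the sentence is loose wording for withdrawal of study medication. If so, it repeats the formulas above it and does no harm. That may be the intent, but the protocol gives the two kinds of withdrawal separate headings, and a programmer following the SAP literally would take the study-withdrawal date.

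A second reply is that Protocol 7.4 divides by the doses due over the whole study, so a denominator that penalises early stopping is legitimate. For a patient who abandons treatment by choice this has some force. But a planned-dose rule would give every day-14 stopper the same denominator. The SAP's denominator moves with the study exit date, so it is neither a planned-dose rule nor an on-treatment rule.

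Third, remaining in the study after a treatment stop is optional under Protocol section 10, so few patients may be affected. Visit-level compliance for intervals completed before the stop is also untouched. Both points stand and limit the size.

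A reader might go further and infer that any adherent patient who stops for an adverse event and stays on is labelled Low. The documents do not support that: with exit on day 56, stops from day 45 onward remain Normal, and for a Visit 4 completer the rule is undefined. A reader might also infer that these patients fall out of the per-protocol population. SAP 5.4 defines that population by major deviations that could affect the primary efficacy analysis plus Week 0 and Week 8 data, and SAP 9.2 has deviations reviewed case by case. Neither mentions the SAP 15 compliance classes.

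**Conclusion.** The point holds in a limited form. SAP 15.1 gives two end points for the same denominator. For patients who stop drug and withdraw from the study later, the one it prescribes understates adherence by 100 × (1 − s/T) percentage points. Misclassification as Low needs off-drug time above 25% of on-drug time. For patients who stop drug and complete Visit 4, the rule has no defined result, and the 25% and 50% figures are one reading of that gap.

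The per-patient figures assume full intake to the stop. The population figures also rest on assumed rates of stopping and staying, for which the documents give no basis. The affected outputs are the percentage, the class and the compliant flag, all descriptive. The mITT definition and the primary DBP test do not use compliance, and any effect on the per-protocol population would need a rule that the documents do not contain. This is a derivation to correct, not a threat to the trial's main conclusion.

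**What to change.** Replace the last sentence of SAP 15.1 with: *for patients who permanently stop, expected tablets are counted to the date of last study medication (End of Study Treatment form)*. SAP 14 already takes that date from this form and SAP 14.1 uses it for exposure, so no new data are needed and the two sections would agree. Replacing the sentence is better than deleting it, because SAP 15.1 does not say where its treatment end date comes from.

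The cost is one sentence and the matching line of programming. The downside is that compliance would no longer reflect early stopping, including stopping by patient choice: someone who abandons treatment after full intake would score 100%. The disposition and withdrawal summary (SAP 9.1), duration of exposure (SAP 14) and adverse events leading to discontinuation of study medication (SAP 18.1.2) are already planned and show early stopping. The adherence table should be read alongside them.

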16. EFFICACY OUTCOMES

16.1. Primary Efficacy

16.1.1. Primary Efficacy Variable & Derivation

The primary efficacy variable is Change in mean sitting DBP between Visit 2 (Week 0) and Visit 4 (Week 8).

16.1.2. Intercurrent Event Handling and Data Imputation for Primary Efficacy Variable

Not Applicable.

16.1.3. Primary Analysis of Primary Efficacy Variable

The primary objective of this study is to test the hypothesis that

H0: There is no change in the sitting DBP prior or post combination therapy.

H1: There is a difference in the sitting DBP prior or post combination therapy.

The primary efficacy analysis will be performed for the mITT population. The above hypothesis will be tested as following:

- Change from baseline in sitting DBP from prior and post combination therapy will be tested using paired t-test. The p-value obtained from the paired t-test will be presented.
- Assumption of Normality will be investigated using Wilk-Shapiro test. If the data is found to be non-Normal, the paired t-test will be replaced by Wilcoxon signed rank test.

Document: \\weedc-vnasc01\Biosdata\Menarini\NebAml\ZZA67778\Biostatistics\Documentation\SAP\SAP_Menarini_MEIN21AmNe-Hyp001_Final_V1.0

Author: [name]

Version Number:

Final V1.0

Version Date:

11Nov2022

Template No.: CS_TP_BS016 Revision 7

Reference: CS_WI_BS005

Effective Date: 01Nov2021

- The primary endpoint will be summarized descriptively using n, mean, median, SD, Q1, Q3, minimum, and maximum.
- Only those patients for whom we have DBP assessment results available at both Week 4 and Week 8 will be considered.

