	To test the covariate effects and the effects of interactions between covariates on the primary efficacy endpoint (change in mean sitting DBP) as well as the first secondary efficacy endpoint (change in mean sitting SBP), a repeated measures general linear model (GLM) will be proposed. The GLM repeated measures procedure provides analysis of variance when the same measurement is made several times on each patient. Age, gender, body mass index, and baseline DBP will be included in the GLM model as covariates. The GLM model will be explained in detail in the Statistical Analysis Plan, approved before database lock.
	All the other continuous secondary/exploratory endpoints will be assessed across different study visits using a paired t-test or independent t-test, as applicable.
	All secondary/exploratory endpoints related to proportion of patients achieving the BP goal at Week 4 and Week 8 will be analyzed descriptively along with the relative 95% CI to assess if there is a significant difference from Week 0 where all patients were uncontrolled.
	Sample size : A total sample size of 216 patients is required to achieve 90% power at a 5% significance level assuming a difference in mean DBP from baseline (Visit 2) to 8 weeks (Visit 4) of 4 mmHg and a standard deviation for this difference of 10 mmHg. The mean change in DBP for the null hypothesis is set equal to 2 mmHg.

[figure not shown]
MENARINI	Corporate Medical Department		
	Р	Protocol Template	
Identification Number	Version Number	State	Effective date
FORM-000050125	2.0, CURRENT	Effective	08 Jan, 2021

A total number of 290 patients will be screened considering 25% of
drop-out rate, to obtain approximately 216 completed patients at the
end of the study (Visit 4).

MENARINI	Corporate Medical Department				
	Pr	otocol Template			
Identification Number	Version Number	State	Effective date		
FORM-000050125	2.0, CURRENT	Effective	08 Jan, 2021		

Study Code: MEIN/21/AmNe-Hyp/001

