## **12.2 Determination of Sample Size**

Considering a screen failure and a drop-out rate of 25% from Visit 1 to Visit 4 (End of Treatment), the number of patients to be screened are 290. Two-hundred and sixteen patients with uncontrolled hypertension, are planned to be included at screening in the assessment period lasting for 8 weeks. A total sample size of 216 patients is required to achieve 90%

NENARINI	Corporate Medical De		rtment	
	P	rotocol Template		
Identification Number	Version Number	State	Effective date	
FORM-000050125	2.0, CURRENT	Effective	08 Jan, 2021	

Study Code: MEIN/21/AmNe-Hyp/001

power at 5% significance level assuming a difference in mean DBP from baseline to 8 weeks of 4 mmHg and a standard deviation (SD) for this difference of 10 mmHg. The mean change in DBP for null hypothesis is set at 2 mmHg.

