### 12.5.2 Primary (efficacy) analysis

The primary efficacy analysis will be conducted on the mITT population. The results will be interpreted for the same population.

The primary endpoint is the change in mean sitting DBP between Visit 2 (Week 0) and Visit 4 (Week 8).

MENARINI	Corporate Medical Department		
	Р	rotocol Template	
Identification Number	Version Number	State	Effective date
FORM-000050125	2.0, CURRENT	Effective	08 Jan, 2021

*Study Code:* MEIN/21/AmNe-Hyp/001

The statistical hypothesis will be defined as below:

H0: There is no change in the sitting DBP prior or post combination therapy.

H1: There is a difference in the sitting DBP prior or post combination therapy.

The above hypothesis will be tested as following:

- Change from baseline in sitting DBP from prior and post combination therapy will be tested using paired t-test. The p-value obtained from the paired t-test will be presented.
- Assumption of Normality will be investigated using Wilk-Shapiro test. If the data is found to be non-Normal, the paired t-test will be replaced by Wilcoxon signed rank test.
- The primary endpoint will be summarized descriptively using n, mean, median, SD, Q1, Q3, minimum, and maximum.

Additionally, a repeated measure general linear model (GLM) will be performed on the primary efficacy endpoint (change in mean sitting DBP) to test the covariate effects and the effects of interactions between the covariates. Age, gender, body mass index, and baseline DBP will be included in the GLM model as covariates. The GLM model will be explained in detail in the Statistical Analysis Plan (SAP), approved before database lock.

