2. STUDY OBJECTIVES AND ESTIMANDS

2.1. Primary Objective

The primary objective is to assess the antihypertensive efficacy of the extemporaneous combination of nebivolol (NEB) 5 mg with amlodipine (AML) 5 mg or AML 10 mg in lowering the sitting DBP between Visit 2 (Week 0) and Visit 4 (Week 8) in patients with uncontrolled BP, previously treated with NEB 5 mg or AML 5 mg monotherapies for at least 4 weeks.

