6.5. Statistical Tests

The default significant level will be (5%); confidence intervals will be 95% and all tests will be two-sided, unless otherwise specified in the description of the analyses.

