6.6. Common Calculations

For quantitative measurements, change from baseline will be calculated as:

- Test Value at Visit X – Baseline Value

And for change between Visit 3 and Visit 4 will be calculated as:

- Test Value at Visit 4 – Visit 3 Value

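### The sample size is calculated against a null DBP fall of 2 mmHg, but the primary test uses a null of 0, so the stated 90% power does not belong to the planned test

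*SAP*

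**What the plan says.** The sizing text appears twice in the protocol with the same inputs: 216 patients, 90% power, 5% significance level, a mean DBP change of 4 mmHg from Visit 2 to Visit 4, and an SD of 10 mmHg for that change. The synopsis adds "The mean change in DBP for the null hypothesis is set equal to 2 mmHg", and section 12.2 adds "The mean change in DBP for null hypothesis is set at 2 mmHg". Neither place gives a reason for the 2 mmHg or says whether the 5% is one-sided or two-sided.

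The analysis text uses another null. Protocol 12.5.2 gives it as "There is no change in the sitting DBP prior or post combination therapy", and SAP 16.1.3 repeats it: "H0: There is no change in the sitting DBP prior or post combination therapy". The reference code in SAP Appendix 1 sets `h0=0` for the paired t-test and `mu0=0` for the signed-rank test that replaces it if normality is rejected. By default under SAP 6.5, "confidence intervals will be 95% and all tests will be two-sided", and SAP 16.1.3 makes no exception for the primary test. The primary objective (SAP 2.1) speaks of lowering DBP and names no threshold. SAP 3.3, which lists changes from the protocol, does not mention the null.

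**The concern.** One primary endpoint has two numerical nulls, and the power figure is attached to the one that will not be tested. The stake is what a positive result means. The trial has no concurrent control, so the size of the fall carries most of the information. A reader who sees a trial sized against 2 mmHg and then a significant p-value may conclude that the fall exceeds 2 mmHg. The planned test does not support that conclusion. SAP 16.1.3 promises a p-value and descriptive statistics but lists no confidence interval for the primary change, so it may not be evident whether 2 mmHg is excluded. If the null is still open when the data are locked in an open-label study, it could also be chosen after the results are known.

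**Working it through.** **Inputs** (Protocol synopsis and 12.2): n = 216, SD = 10, assumed fall 4, sizing null 2, level 5%. From Protocol 12.5.2, SAP 16.1.3 and SAP 6.5: one-group paired t-test, null 0, two-sided.

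**Formulas.** SE = SD/√n = 10/√216 = 0.6804. Noncentrality = (true fall − null)/SE, with 215 degrees of freedom. Power comes from the noncentral t distribution. The normal approximation is n = [SD × (z_α + z_power)/(true fall − null)]².

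**Reproducing 216.** Difference from null = 4 − 2 = 2, noncentrality = 2/0.6804 = 2.94.

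- One-sided 5%: the normal approximation is [10 × (1.645 + 1.282)/2]², which gives 215. The exact t calculation gives 216 (power 0.9007 at 216, 0.8995 at 215).
- Two-sided 5%: the normal approximation is [10 × (1.960 + 1.282)/2]², which gives 263. The exact t calculation gives 265 (264 gives 0.8993). Power at 216 is 0.8330.

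From the stated single-group inputs, 216 is therefore reached only with a one-sided 5% test. That is an inference, since the sizing text is silent on sidedness. A two-sample, one-sided 5% formula for a difference of 4 mmHg also gives 108 per group (0.9006; 107 per group gives 0.8982), but it ignores both the stated null of 2 and the paired design. Two-sided, it would need 133 per group.

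**The planned test.** Null 0, so the difference is 4 and the noncentrality is 4/0.6804 = 5.88. Two-sided 5% power is 0.99995. Only 68 patients would give 90% (67 gives 0.8973). With 216, 90% power is already reached at a true fall of 2.22 mmHg. At a true fall of exactly 2 mmHg, the sizing null, the planned test rejects with probability 0.833.

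**Smallest significant observed fall** (SD 10, n = 216). The half-width is 1.971 × 0.6804 = 1.341 for a 95% CI and 1.652 × 0.6804 = 1.124 for a 90% CI.

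| Test | Power at 4 mmHg | Smallest significant fall |
|---|---|---|
| Null 0, two-sided 5% (planned) | over 99.99% | 1.34 mmHg |
| Null 2, one-sided 5% | 90.1% | 2 + 1.124 = 3.12 mmHg |
| Null 2, two-sided 5% | 83.3% | 2 + 1.341 = 3.34 mmHg |

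**Example.** An observed fall of 1.5 mmHg gives t = 1.5/0.6804 = 2.20, p = 0.029, 95% CI 0.16 to 2.84. It is significant against 0 but does not exclude 2.

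**The case against.** The best defence is that the analysis side is coherent. Protocol 12.5.2 and SAP 16.1.3 agree, the objective sets no threshold, the code tests 0, and no passage promises a claim beyond 2 mmHg. Type I error, the estimate and the planned decision are unaffected, and the power statement errs in the safe direction. If the assumed 4 mmHg is observed with SD 10, the 95% CI is 4 ± 1.34, or 2.66 to 5.34, which excludes 2 anyway.

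Much of this stands. The test is sound for its own null, and 0 is the better-supported reading. The conflict lies within the protocol, and the SAP only repeats the protocol's hypothesis, so SAP 3.3 had no change to log. The code is a generic template, so it corroborates the null of 0 but does not establish it independently. What does not stand is leaving the text as it is. The same 216 patients carry a stated power that is wrong for the test to be run, and any observed fall between 1.34 and about 3.1 mmHg is positive under one written null and negative under the other.

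**Conclusion.** The concern holds. The stated 90% power describes a test against 2 mmHg, apparently one-sided, while the planned test is two-sided against 0 with over 99.99% power at the assumed effect. The fault is in what the documents say the test shows, not in its validity or its chance of success.

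The figures assume SD 10 and 216 analysed patients. The protocol is not consistent on whether 216 enter the assessment period (12.2) or complete it (synopsis). If 25% of 216 were lost, leaving 162, power at 4 mmHg would be 99.9% against 0 and 71.6% against 2 (two-sided). The conclusion would not change. The existence of two nulls is explicit in the text; the one-sidedness of the sizing is inferred from the arithmetic.

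**What to change.** Before database lock, state one null and one sidedness for the primary DBP test in both documents, restate the power to match, and report the mean reduction with its confidence interval.

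**Route (a), null 0, which the documents favour.** Keep the test and the code. Amend the synopsis and Protocol 12.2 to remove the 2 mmHg null and say that 216 patients give over 99.99% power at 4 mmHg (SD 10, two-sided 5%). Word this as a correction, not as a new justification of 216. The cost is a protocol amendment under 12.6 and giving up any claim beyond 2 mmHg based on the p-value.

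**Route (b), null 2.** Restate H0 as a mean fall of 2 mmHg or, if one-sided, of 2 mmHg or less, and restate H1 to match. Change the code for the primary DBP test only: `h0=2` for Visit 2 minus Visit 4, and `mu0=-2` for change from baseline, which SAP 6.6 defines as visit value minus baseline. Leave the generic code at 0 for the other tests.

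- Two-sided 5%: power is 83.3%, and 90% would need 265 patients. Decide on the 95% CI.
- One-sided 5%: power is 90.1%. Write it as an exception to SAP 6.5, use `sides=U` for Visit 2 minus Visit 4, and report a 90% CI or a one-sided 95% limit. Interval and test must match: an observed fall of 3.2 mmHg has one-sided p = 0.040 and a 90% CI lower limit of 3.2 − 1.124 = 2.08, but a 95% CI lower limit of 3.2 − 1.341 = 1.86.
- Fallback: where "the paired t-test will be replaced by Wilcoxon signed rank test", base the decision on the signed-rank test against the same null, not on the confidence limit for the mean. PROC UNIVARIATE gives a two-sided p-value, so for a one-sided test state that it is halved when the statistic points to a larger fall.

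Route (b) changes the primary analysis, so Protocol 12.7 requires a substantial amendment. It would come late in an open-label study (SAP dated 11 November 2022, last patient out planned for the beginning of December 2022) and would raise the smallest significant fall from 1.34 to 3.12 or 3.34 mmHg. The reason for the choice must be documented before lock.
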